6.3. Lifestyle Restrictions

Study participants should be instructed not to donate blood or blood products during the study.

6.4. Screen Failures

Individuals who do not meet the criteria for participation in this study (screen failure) maybe rescreened. Individuals may be rescreened up to 3 times. The interval between rescreenings should be at least 1 week. Each time rescreening is performed the individual must sign a new informed consent form (ICF) and will be assigned a new identification number. Patients who have had previous screening TB tests as per protocol within 3 months of their rescreening date of consent do not need to repeat these procedures but may do so at the discretion of the investigator.

Individuals may be rescreened as follows:

- Patients who test positive for latent TB at screening may be rescreened following appropriate treatment as described in Section [9.4.5.2](#).
- Patients who do not qualify at screening under Exclusion Criteria [10] (active or recent infection) may be rescreened as described in Section [6.2](#).

7. Treatments

7.1. Treatments Administered

The investigator (or his/her designee) is responsible for explaining the correct use of the investigational agent(s) to the patient and/or patient's caregiver, verifying that instructions are followed properly, maintaining accurate records of investigational product dispensing and collection, and returning all unused medication to Lilly or its designee at the end of the study. Further instructions regarding administration of the investigational product are provided below in this section.

Patients will be instructed to contact the investigator as soon as possible if he or she has a complaint or problem with the investigational product so that the situation can be assessed.

The Induction Dosing Period (Period 2) begins at Week 0 (baseline; Visit 2) when patients receive a starting dose of 160 mg ixekizumab as 2 SC injections. For the remaining doses, 80 mg is administered Q2W. All doses are administered as SC injections.

Administration of Investigational Product

Training: For training purposes, the proper procedures for administration of the investigational product and administration of the initial injection will be performed by the investigator or his/her designee at Week 0 (Visit 2) and the second injection of investigational product can be self-administered by the patient under the supervision of the investigator at Week 0 (Visit 2). Study drug must be administered under the supervision of the investigator until the investigator judges the patient sufficiently competent to perform the self-injections independently. After this time, patients will be allowed to self-inject alone.

Administration: All subsequent injections can be administered by the patient. If a patient is unable to perform the injection, the investigator or a caregiver, may inject the investigational product. In this case, the caregiver will also be trained to inject the study drug under supervision of the investigator until the investigator judges the caregiver sufficiently competent to inject.

A dose of investigational product will consist of 1 SC injection of ixekizumab (except Week 0). Possible injection sites include the abdomen, thigh, and upper arm. The injection site should not be in a psoriatic lesion and should be rotated to another area for subsequent doses.

Syringes should be at room temperature prior to injection (refer to Manual Syringe Directions for Use provided by the sponsor).

Throughout their participation in the study, enrolled patients will record information in a Study Drug Administration Log, including the date, time, injection site, and location of patient at time of administration of investigational product (for treatment compliance), who administered the investigational product, and the reason if investigational product was not fully administered in a Study Drug Administration Log. As needed, patients may use the log to record other information about the injection. At each visit, the investigator will review the log to confirm whether the self-injections were successfully performed.

Observation: Patients should remain under observation for at least 1 hour after dosing at Week 0 (Visit 2) to monitor for safety.

Table RHCV.3. Treatment Periods

| Treatment Period | Weeks | Dose | Description |
|---|---------------------|---|---|
| Induction Dosing Period (Period 2) and Maintenance Dosing Period (Period 3) | 0 to 12 12 to 20 | Ixekizumab 160 mg initially, followed by ixekizumab 80 mg Q2W | A starting dose of 160 mg (Week 0) given as 2 SC injections followed by 80 mg given as 1 SC injection Q2W (Weeks 2, 4, 6, 8, 10, 12, 14, 16 and 18) |

Abbreviations: Q2W = every 2 weeks; SC = subcutaneous.

The investigator or his/her designee is responsible for the following:

- explaining the correct use of the investigational agent(s) to the site personnel
- verifying that instructions are followed properly
- maintaining accurate records of investigational product dispensing and collection
- at the end of the study returning all unused medication to Lilly, or its designee, unless the sponsor and sites have agreed all unused medication is to be destroyed by the site, as allowed by local law.

7.1.1. Packaging and Labelling

The ixekizumab solution for injection will be supplied by the sponsor or its designee in accordance with current Good Manufacturing Practices (cGMP). Ixekizumab will be supplied as an injectable solution in 1-mL, single-dose, disposable manual prefilled syringes. Each syringe of ixekizumab is designed to deliver ixekizumab 80 mg. Syringes will be supplied in cartons, with the appropriate quantity of syringes specific to the planned dispensing schedule of the investigational product.

Clinical trial materials will be labeled according to the country's regulatory requirements. All investigational products will be stored, inventoried, reconciled, and destroyed according to applicable regulations.

Investigational products will be supplied by Lilly or its representative, in accordance with cGMP, and will be supplied with lot numbers and expiration dates.

The investigational product should be stored at 2°C to 8°C in its original carton to protect from light. Investigational product should not be frozen. Sites will be required to monitor temperature of the on-site storage conditions of the syringes.

7.2. Method of Treatment Assignment

Patients are assigned to treatment and will receive their assigned treatment as outlined in Section 7.1.

7.2.1. Selection and Timing of Doses

Investigational product should be administered at approximately the same time each day, as much as possible. For injections not administered on the scheduled day of the week from Week 0 to Week 18, the missed dose should be administered within 4 days of the scheduled day. Dates of subsequent study visits should not be modified according to this delay.

The actual time of all dose administrations will be recorded in the patient's case report form (CRF).

7.3. Blinding

This is an open-label study.

7.4. Dosage Modification

Dose adjustments are not permitted in this study.

7.5. Preparation/Handling/Storage/Accountability

The investigator or his/her designee is responsible for the following:

- confirming appropriate temperature conditions have been maintained during transit for all study treatment received and any discrepancies are reported and resolved before use of the study treatment.
- ensuring that only participants enrolled in the study may receive study treatment and only authorized site staff may supply or administer study treatment. All study treatments must be stored in a secure, environmentally controlled, and monitored (manual or automated) area in accordance with the labeled storage conditions with access limited to the investigator and authorized site staff.
- the investigator, institution, or the head of the medical institution (where applicable) is responsible for study treatment accountability, reconciliation, and record maintenance (such as receipt, reconciliation and final disposition records).

Detailed instructions regarding supplies and preparation and handling of investigational products will be provided by the sponsor.

Investigational products will be supplied by Lilly or its representative, in accordance with cGMP and will be supplied with lot numbers, expiry dates, and certificates of analysis, as applicable. All investigational products will be stored, inventoried, reconciled, or destroyed according to applicable regulations.

The investigational product should be stored at 2°C to 8°C in its original carton to protect from light. Investigational product should not be frozen. Sites will be required to monitor temperature of the on-site storage conditions of the syringes.

7.6. Treatment Compliance

Every attempt will be made to select patients who have the ability to understand and comply with instructions. The investigator is responsible for discussing methods to ensure high treatment compliance with the patient before administration of study treatment.

Throughout their participation in the study, enrolled patients will record information in a Study Drug Administration Log, including the date, time, injection site, and location of patient at time of administration of investigational product (for treatment compliance), who administered the investigational product, and the reason if investigational product was not fully administered. As needed, patients may use the log to record other information about the injection. At each visit, the investigator will review the log to confirm whether the self-injections were successfully performed.

Patient compliance with study drug administration will be assessed at each visit. Compliance will be assessed by direct questioning, and counting returned syringes. Deviation(s) from the prescribed dosage regimen should be recorded in the CRF.

7.7. Concomitant Therapy

The list of excluded medications and procedures is provided in [Appendix 6](#).

The following medications **will not** be permitted during the course of the study (from obtaining written Informed Consent to study completion):

- Ps therapy as described in the inclusion/exclusion criteria (Sections [6.1](#) and [6.2](#)) with the exceptions described below.
 - Any biologic therapy specified in Section [6.2](#)
 - Concomitant medications as described in the inclusion/exclusion criteria (Sections [6.1](#) and [6.2](#))
 - Live vaccines
 - Phototherapy.

The following medications **will be** permitted during the course of the study:

- Vaccine: Use of nonlive seasonal vaccinations and/or emergency vaccination (such as rabies or tetanus vaccinations) is allowed.
- Methotrexate and oral retinoids will be permitted before and during the study if the patient has been using such medication before starting the study and if doses are not greater than that of baseline.
- Oral corticosteroids will be permitted before and during the study, if the patient has been using such medication before starting the study and if average daily doses are not greater than 10 mg/day of prednisone or its equivalent.

- Cyclosporine will be permitted, if the patient has been using such medication before starting the study and if daily doses are not greater than that of baseline.
- Topical steroids: topical steroids (all classes) will be permitted.
- Granulocyte-monocyte adsorption apheresis (GMA): use of GMA is allowed.
- Other Concomitant Therapies: topical treatments will be permitted.

8. Discontinuation Criteria

8.1. Discontinuation from Study Treatment

8.1.1. *Permanent Discontinuation from Study Treatment*

Possible reasons leading to permanent discontinuation of investigational product:

- **Patient Decision**
 - the patient requests to discontinue investigational product.
- **Discontinuation due to a hepatic event or liver test abnormality.** A patient who is discontinued from investigational product due to a hepatic event or liver test abnormality should have additional hepatic safety data collected via CRF.

Discontinuation of the investigational product for abnormal liver tests **should be** considered by the investigator when a patient meets one of the following conditions after consultation with the Lilly designated medical monitor:

- ALT or AST >8X ULN
- ALT or AST >5X ULN for more than 2 weeks
- ALT or AST >3X ULN and total bilirubin level (TBL) >2X ULN or international normalized ratio (INR) >1.5
- ALT or AST >3X ULN with the appearance of fatigue, nausea, vomiting, right upper-quadrant pain or tenderness, fever, rash, and/or eosinophilia (>5%)
- alkaline phosphatase (ALP) >3X ULN
- ALP >2.5X ULN and TBL >2X ULN
- ALP >2.5X ULN with the appearance of fatigue, nausea, vomiting, right quadrant pain or tenderness, fever, rash, and/or eosinophilia (>5%)
- In addition, a patient who meets any one of the following criteria should be discontinued from the investigational product and conduct ETV, and discontinue from the study:
 - Absolute neutrophil (segmented) counts (see safety monitoring for neutropenia; Section 9.4.6.1):
 - <500 cells/ μ L
 - \geq 500 and <1000 cells/ μ L (based on 2 test results; the second test performed within 1 week from knowledge of the initial result).
 - \geq 1000 and <1500 cells/ μ L (based on 3 test results as specified in Section 9.4.6.1) - AND - an infection that is not fully resolved.
 - Total WBC count <2000 cells/ μ L (<2.00 x 10³/ μ L).
 - Lymphocyte count <500 cells/ μ L (<0.50 x 10³/ μ L).
 - Platelet count <50,000 cells/ μ L (<50 x 10³/ μ L).

- The patient experiences a severe AE, an SAE, or a clinically significant change in a laboratory value occurs that, in the opinion of the investigator, merits the discontinuation of the investigational product.
- Clinically significant systemic hypersensitivity event following administration of investigational product that does not respond to symptomatic medication or results in clinical sequelae.
- The patient becomes pregnant.
- The patient develops a malignancy (Note: patients may be allowed to continue if they develop no more than 2 non-melanoma skin cancers during the study).
- The patient has a change in disease phenotype at any time.
- It is recommended that the patient be assessed by an appropriately trained professional to assist in deciding whether the patient is to be discontinued from study treatment if:
 - The patient develops active suicidal ideation with some intent to act with or without a specific plan (yes to question 4 or 5 on the “Suicidal Ideation” portion of the C-SSRS),
 - OR-
 - The patient develops suicide-related behaviors as recorded on the C-SSRS, then it is recommended that the patient be assessed by a psychiatrist or appropriately trained professional to assist in deciding whether the patient is to be discontinued from the study.
 - The patient develops active TB or HIV/ acquired immunodeficiency syndrome (AIDS) during the study.
 - The patient becomes HBV (DNA) or HCV RNA positive. The patient should be referred to a specialist physician (see Sections 9.4.5.4 and 9.4.5.5).
- **Discontinuation due to Allergic Reactions or Hypersensitivity Events**
 - The investigator, after consultation with the sponsor-designated medical monitor, determines that a clinically significant hypersensitivity reaction has occurred. A clinically significant systemic hypersensitivity reaction is one that occurs after administration of the investigational intervention (for example, drug-related symptomatic bronchospasm, allergy-related edema/angioedema, or hypotension) and requires parenteral medication, does not respond to symptomatic medication, results in clinical sequelae, or is an anaphylactic reaction.

Patients discontinuing from the investigational product prematurely for any reason should complete AE and other follow-up procedures per Section 2 (Schedule of Activities), Section 9.2 (Adverse Events), and Section 9.4 (Safety) of this protocol.

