9.4.6.4. Allergic Reactions and Hypersensitivity Events

All biologic agents carry the risk of systemic allergic/hypersensitivity reactions. Clinical manifestations of these reactions may include but are not limited to:

- Skin rash
- Pruritus (itching)
- Dyspnea
- Urticarial (hives)
- Angioedema (for example, swelling of the lips and/or tongue)
- Hypotension
- Anaphylactic reaction

Participants with clinical manifestations of systemic allergic/hypersensitivity reactions should be treated per local standard of care. Additional data describing each symptom should be provided to the sponsor in the CRF.

In case of anaphylaxis or generalized urticaria, additional blood samples should be collected as close as possible to the onset of the event (see Section 9.4.4 Immunogenicity Assessments). Follow-up samples should be obtained at the next regularly scheduled visit or 4 weeks after the event, whichever is later. The lab results are provided to the sponsor via the central laboratory.

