### **6.3.1. Nonresponder Imputation (NRI)**

Categorical binary efficacy and health outcomes variables will be summarized using a nonresponder imputation (NRI) method. Patients will be considered a nonresponder if they do not meet the clinical response criteria or have missing clinical response data at the scheduled time point. All patients who discontinue study treatment at any time prior to the scheduled visit for any reason will be defined as nonresponders regardless of study continuation without study treatment at the visit. Enrolled patients without at least 1 post-baseline observation will also be defined as nonresponders.

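### Protocol 8.1.1 gives two overlapping hypersensitivity discontinuation criteria that differ in scope, in the consultation step and in whether the patient leaves the study

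*Protocol*

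**What the plan says.** Protocol 8.1.1 opens with a general lead-in: "Possible reasons leading to permanent discontinuation of investigational product". Two separate hypersensitivity texts follow.

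The first is a bullet in the list of criteria for which a patient "should be discontinued from the investigational product and conduct ETV, and discontinue from the study". It reads: "Clinically significant systemic hypersensitivity event following administration of investigational product that does not respond to symptomatic medication or results in clinical sequelae". It mentions no consultation.

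The second has its own heading on allergic reactions at the end of the section. It applies when "The investigator, after consultation with the sponsor-designated medical monitor, determines that a clinically significant hypersensitivity reaction has occurred". It then explains the term: a clinically significant systemic reaction is one that follows dosing and "requires parenteral medication, does not respond to symptomatic medication, results in clinical sequelae, or is an anaphylactic reaction". It does not mention discontinuation from the study.

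Neither text refers to the other.

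**The concern.** The same term, clinically significant, is narrowed by two conditions in one place and defined by four in the other. The two places also attach different procedures and different consequences. A site dealing with a serious reaction could follow either text and act properly by it, yet handle the patient differently from another site.

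What is at stake is consistent handling of a safety event that the protocol itself lists among its adverse events of special interest (9.2.2). The case that shows the gap most clearly is an anaphylactic reaction that responds to treatment and leaves no sequelae. The same gap exists for a non-anaphylactic reaction that needs parenteral treatment and then resolves.

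**Working it through.** There is no planned figure to reproduce, because the question concerns the logic of two texts. The check has three steps.

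**Step 1: scope.** Take a systemic reaction after dosing and give it four yes/no attributes from 8.1.1:

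- P: parenteral treatment was needed
- N: symptomatic treatment failed
- S: sequelae followed
- A: the reaction was anaphylactic

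First text: N or S. Second text: P or N or S or A.

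- Possible combinations: 2 × 2 × 2 × 2 = 16.
- The first text fails only when N and S are both absent. That leaves P and A free, so 2 × 2 = 4 combinations fail and 16 − 4 = 12 meet it.
- The second text fails only when all four are absent, so 16 − 1 = 15 meet it.
- Combinations that meet the second but not the first: 15 − 12 = 3. They are P only, A only, and P with A.
- Combinations that meet the first but not the second: 0. The criteria are nested.

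The first text also says clinically significant. Putting the second text's definition into it gives (P or N or S or A) and (N or S), which reduces to N or S, so the count stays at 12. These are counts of logical combinations, not frequencies of events.

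**Step 2: procedure and consequence.**

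| Feature | First text | Second text |
|---|---|---|
| Force | Patient should be discontinued | Listed as a possible reason |
| Medical-monitor consultation | Not mentioned | Precedes the determination |
| Stops product | Yes | Yes, if so determined |
| Early termination visit | Stated | Not stated here, but follows from Protocol 5.1 |
| Leaves the study | Stated | Not stated |

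The procedural difference is not confined to the 3 unmatched combinations. The 12 that meet both texts also have two routes, one with consultation and one without.

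**Step 3: is this reconciled elsewhere?** Two other places bear on it.

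- The severe or serious adverse event bullet in 8.1.1 could capture anaphylaxis, but only where the event, "in the opinion of the investigator, merits the discontinuation of the investigational product". It stands in the same list as the first text, so it carries study discontinuation. It adds a discretionary route and does not settle which of the two hypersensitivity texts governs.
- Section 9.4.6.4 says "Participants with clinical manifestations of systemic allergic/hypersensitivity reactions should be treated per local standard of care" and then deals with data and blood samples. It gives no stopping criterion and does not point back to 8.1.1.

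**The case against.** The best defence is that the two texts do not contradict each other on stopping. Both stand under one lead-in that lists possible reasons, and they are nested, so meeting either is a listed ground for stopping product. Responding anaphylaxis is expressly named in the second text. This stands. A reader might infer that such a patient has to stay on product because the narrower bullet is not met. The documents do not say so: the first list states who should be discontinued and does not exclude other reasons.

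A coherent reading is also available. The second text defines the reaction and allows product to be stopped after consultation; the first picks out the worse subset and adds departure from the study. That may be what was meant, but the protocol does not state it, and it leaves open whether consultation is needed when both texts apply.

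The early termination visit is not a real difference. Protocol 5.1 sends every treated patient who stops treatment to that visit. It might be argued that the visit ends participation on either route. However, SAP 6.3.1 provides for patients who stay in the study off treatment, and SAP 6.7 tabulates treatment and study discontinuation separately, so the documents keep the two apart.

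Finally, such events should be few. Protocol 3.3 reports no serious adverse events and no discontinuations for adverse events in these two diseases under the initially approved regimen. This limits how often the inconsistency would matter, but does not remove it.

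**Conclusion.** The point holds as an inconsistency in a safety discontinuation rule. Two of the second text's four conditions are missing from the first, and the texts differ on whether stopping is directed or left to a determination, whether consultation comes first, and whether the patient leaves the study. The documents give no rate for qualifying reactions, so no frequency can be attached. The conclusion assumes that the first hypersensitivity bullet belongs to the list headed by the instruction to stop product and leave the study, which is how the section reads in sequence.

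A reader might go further and infer an effect on the primary endpoint, since SAP 6.3.1 says "All patients who discontinue study treatment at any time prior to the scheduled visit for any reason will be defined as nonresponders". With the target minimum of 5 continuing patients per disease, one patient is 1/5, or 20 percentage points. The documents do not support presenting that as the size of this problem:

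- Under SAP 6.11.1 the primary counts a response at any of Weeks 14, 16, 18 or 20 or at the early termination visit, so a response reached before stopping can still count.
- A patient who stops in Period 2 never enters the Maintenance Dosing Period Population.
- The same 1/5 would arise from any discontinuation, for any reason, that cost a response.
- The primary is reported as a number of patients, with no inference.

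Any effect on efficacy is incidental. The case for correction rests on consistent handling of a serious reaction.

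**What to change.** Reconcile the two texts in Protocol 8.1.1 into one hypersensitivity criterion. It should state once:

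- which reactions it covers
- whether discontinuation is directed or left to a determination
- whether the medical monitor is consulted first
- whether the consequence is stopping product only or also leaving the study

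Add a cross-reference from 9.4.6.4. Which clinical rule should stand is for the sponsor's medical team; this review takes no view on it.

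The cost is a wording correction in one section and one cross-reference. Sample size, visit schedule and planned analyses need no change.
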